7.8.4 Sensory Questionnaire

A sensory questionnaire (SQ) will be completed by each subject within 60 minutes after the *ad libitum* use session on Days 1 through 4 (adapted from (22)). The SQ assesses the subject's opinion on the following sensory parameters:

- Puff information i.e., how they liked the puffs, harshness of puffs, and similarity to own brand;
- Strength of puffs on tongue, nose, mouth, windpipe, and chest.

7.8.5 Cough Assessment

Subjects will be asked if they have experienced a regular need to cough, e.g., whether they have coughed several times in the previous 24 hours prior to assessment. If the answer is 'yes', they will be asked to complete a cough assessment questionnaire (which includes a VAS, three Likert scales, and an open question).

The VAS will assess how bothersome cough is to the subject ranging from 'not bothering me at all' to 'extremely bothersome'.

Furthermore, subjects will be asked to assess the intensity and frequency of cough and the amount of sputum production on Likert scales:

- The intensity of cough will be assessed on a 5-point Likert scale ranging from 1 to 5:
1 = very mild; 2 = mild; 3 = moderate; 4 = severe; 5 = very severe.
- The frequency of cough will be assessed on a 5-point Likert scale ranging from 1 to 5:
1 = rarely; 2 = sometimes; 3 = fairly often; 4 = often; 5 = almost always.
- The amount of sputum production will be assessed on a 4-point Likert scale ranging from 0 to 3:
0 = no sputum; 1 = a moderate amount of sputum; 2 = a larger amount of sputum; 3 = a very large amount of sputum.

Cough assessment will be conducted at Admission prior to product test and 24 hours (± 1 hour) after product use (T_0 fix) for each variant (Day 2 through Day 5). Cough assessment should be done in the morning prior to any product use.

Confidentiality Statement

Data and information contained in this document are considered to constitute trade secrets and confidential commercial information, and the legal protections provided to such trade secrets and confidential information are hereby claimed under the provisions of applicable law. No part of this document may be publicly disclosed without the written consent of Philip Morris Products S.A.

7.9 Other Study Procedures

7.9.1 Human Puffing Topography

Human puffing topography involves the measurement of each subject's unique way of using P3P using the HPT SODIM® device. The HPT SODIM® device, model SPA/M (SODIM® Instrumentation, Fleury les Aubrais, France) is a device which is used to measure puffing topography. It consists of a special sample holder with mechanical adapter and a data logger. Both the sample holder and the mechanical adapter are associated prior the activation of the P3P, and its insertion into the mechanical adapter using a depth adjustment tool. The sample holder is connected by 2 narrow tubes to the portable data logger/recording system. Any malfunction of the HPT SODIM® portable device will be documented in the appropriate log.

The HPT SODIM® device has to be used for every P3P used for all subjects from Day 1 to Day 4, both during the fixed puffing and the *ad libitum* use period. For each subject, one HPT Device will be assigned at Day 1 which will be used by that subject for all HPT assessments. A replacement device will be provided in case of malfunction of the device assigned.

The Sponsor will provide training on the use of the HPT SODIM® device to the site collaborators which will be responsible for the HPT assessment. All HPT SODIM® devices will be returned to the Sponsor after completion of the study.

The HPT SODIM® device measures and records the flow rate and other per-puff parameters listed in Appendix D. From the per-puff parameters, per-product use experience parameters, representing average or total values per product, will be derived (Appendix D).

Prior to calculation of the per-product use experience parameters, the Sponsor's HPT group will process, validate and discard any invalid data, as per the Sponsor's SOPs. The Sponsor will provide copies of both the raw and validated HPT datasets to the Investigator. Only valid data for the per-puff and per-product use experience parameters will be part of the study database and will be analyzed.

7.9.2 Weighing of P3P Products

From Day 1 to Day 4, each P3P used should be weighed before product use (after assembly) and as early as possible (but within maximum 75 minutes) after the end of product use. The pre- and post- product use weight and time of weighing will be recorded in the CRF.

Confidentiality Statement

Data and information contained in this document are considered to constitute trade secrets and confidential commercial information, and the legal protections provided to such trade secrets and confidential information are hereby claimed under the provisions of applicable law. No part of this document may be publicly disclosed without the written consent of Philip Morris Products S.A.

8 ADVERSE EVENTS

8.1 Definitions

8.1.1 Adverse Events

An adverse event (AE) is defined as any unfavourable and unintended sign (including an abnormal laboratory finding), symptom, or disease temporally associated with the use of a product or a study procedure, whether or not related to the product or the study procedure. Careful Investigator's medical judgment is required to establish whether a clinical finding (including an abnormal laboratory result) is a true AE or just a manifestation of a preexisting health – related condition.

8.1.2 Serious Adverse Events

An SAE is any untoward medical occurrence that at any dose:

- results in death,
- is life-threatening,
- requires inpatient hospitalization or prolongation of existing hospitalization,
- results in persistent or significant disability/incapacity, or,
- is a congenital anomaly/birth defect.

Important medical events that may not result in death, be life-threatening, or require hospitalization may be considered an SAE when, based on appropriate Investigator's medical judgment, they may jeopardize the subject or the subject may require medical or surgical intervention to prevent one of the outcomes listed in the above definitions.

"Life-threatening" means that the subject was at immediate risk of death from the event. It might have caused death if it had occurred in a more serious form.

8.1.3 Conditions Existent Before the Start of the Period of Collection (ICF Signature)

Clinical conditions that existed before the start of the period of collection (concomitant disease), and whose severity or frequency remained unchanged after that point, should not be considered AEs and should not be captured as such. This includes medical therapies or surgical interventions that had been planned before the start of the period of collection regardless of involving admissions to hospital, if the medical condition to be addressed did not get worse after the start of the collection period. Otherwise, any medical condition that existed before the start of the period of collection and whose severity or frequency increased after that point is to be captured as an AE or SAE, depending on the seriousness criteria met.

Confidentiality Statement

Data and information contained in this document are considered to constitute trade secrets and confidential commercial information, and the legal protections provided to such trade secrets and confidential information are hereby claimed under the provisions of applicable law. No part of this document may be publicly disclosed without the written consent of Philip Morris Products S.A.

8.2 Collection and Reporting of Adverse Events

8.2.1 Collection of Information

Any non-serious AE occurrence during the study must be documented in the subject's medical records in accordance with the Investigator's normal clinical practice and on the AE page of the CRF. SAEs that occur during the study must be documented in the subject's medical record, on the AE CRF, and on the SAE form.

AEs should be collected mainly via face-to-face interview with the subject through spontaneous reporting or by the use of consistent, open, non-directive questions from the investigator(s) or designee(s) (e.g., "Have you had any health problems since you were last asked? or "How have you been feeling since you were last asked?").

Information recorded will include: verbatim description of the AE/SAE, start and stop dates, seriousness, severity (intensity), action taken (e.g., whether or not the AE/SAE led to the subject's discontinuation from the study), and outcome (e.g., resolved, stabilized).

Information to be recorded about an AE/SAE should include, whenever possible, onset and resolution dates and times, circumstances leading up to the event, clinical elements such as clinical course, specific vital signs and test results that may explain the pathophysiology of the event, as well as alternative explanations to its occurrence.

Whenever a medically meaningful diagnosis is available to comprise a set of reported signs and/or symptoms, it should be preferentially provided as the AE or SAE term, rather than the individual signs and/or symptoms. Otherwise, each one of those signs and/or symptoms should be reported separately as event terms.

8.2.2 Period of Collection

AEs (including SAEs) will be collected from the time of ICF signature until the EOS.

During a 7-day Safety Follow-Up Period there will be recording of spontaneously reported new AEs/SAEs and follow-up of ongoing AEs/SAEs by the study site. In general, AEs will be followed-up until resolved, stabilized (i.e., no worsening of the event), or a plausible explanation for the event has been found and until the end of the study.

Any AEs or SAEs that are ongoing at the end of the Safety Follow-Up Period will be managed as described in section 8.2.6.

SAEs spontaneously reported to the Investigator after the end of the Safety Follow-Up Period and considered related to the investigational product must also be reported to the sponsor.

8.2.3 Intensity of Adverse Event

The Investigator must assess the intensity of each reported AE according to the following grading scale:

Confidentiality Statement

Data and information contained in this document are considered to constitute trade secrets and confidential commercial information, and the legal protections provided to such trade secrets and confidential information are hereby claimed under the provisions of applicable law. No part of this document may be publicly disclosed without the written consent of Philip Morris Products S.A.

Table 5 Intensity of Adverse Events

Mild:	Easily tolerated, not interfering with normal everyday activities
Moderate:	Interferes with normal everyday activities, but the subject is still able to function
Severe:	Incapacitating and requires medical intervention

8.2.4 Relationship to Investigational Product and Relationship to Study Procedures

The Investigator must assess the causal relationship between the exposure to the IP and each of the reported AEs, using the classification system and the criteria described below. The same assessment must be made separately to assess the causal relationship between the study procedures and each of the reported AEs:

Not related: The temporal relationship of the adverse event to IP administration or study procedure(s) makes a causal relationship unlikely, or concomitant medication, therapeutic interventions, or underlying conditions provide a sufficient explanation for the observed event.

Related: The temporal relationship of the adverse event to IP or study procedure(s) makes a causal relationship possible, and concomitant medication, therapeutic interventions, or underlying conditions do not provide a sufficient explanation for the observed event.

8.2.5 Expectedness

Any AE assessed as related to the IP will be assessed for its expectedness. An AE will be regarded as “unexpected” if its nature or severity is not consistent with information already recorded about the IP P3P in section 6.5 of the current Investigator’s Brochure (9).

8.2.6 Follow-up of Non-serious and Serious Adverse Events

Any non-serious AE that is ongoing at the time of Discharge or early termination will be followed-up by the Investigator during the Safety Follow-Up Period until it has been resolved, stabilized (i.e., no worsening of the condition), or an acceptable explanation has been found (e.g., a chronic condition).

At the end of the Safety Follow-Up Period, all ongoing non-serious AEs will be documented as “ongoing” and no further follow-up information will be sought for on them by the Investigator. At that point, the Investigator will assess whether the subject should be referred to his/her General Practitioner to have their ongoing AEs addressed accordingly.

All SAE will be followed up by the Investigator or designee, despite their continuation after the end of the Safety Follow-Up Period, until their resolution, stabilization (i.e., no worsening of the condition), or an acceptable explanation has been found (e.g., a chronic condition).

Confidentiality Statement

Data and information contained in this document are considered to constitute trade secrets and confidential commercial information, and the legal protections provided to such trade secrets and confidential information are hereby claimed under the provisions of applicable law. No part of this document may be publicly disclosed without the written consent of Philip Morris Products S.A.

8.3 Reporting of Serious Adverse Events

Any SAE observed during the period of collection by any of the parties involved in this study (including the Investigational site personnel) must be reported by that party within 24 hours of first awareness to UBC Pharmacovigilance, as described in the respective safety management plan (SMP).

SAEs considered related to the IP and observed by, or reported to, any of the parties involved in this study (including the Investigational site personnel) after the period of collection must also be reported by that party within 24 hours of first awareness to UBC Pharmacovigilance for safety surveillance purposes.

All the SAE report forms must be either faxed or sent as an attachment to an e-mail message to UBC Pharmacovigilance:

UBC Pharmacovigilance:	Fax number:	[REDACTED]
	E-mail:	[REDACTED]
	Address:	United BioSource Corporation [REDACTED] [REDACTED] [REDACTED]

As further information regarding an already reported SAE becomes available to any of the parties involved in this study, such follow-up information should be reported on a new SAE report form, marked as a follow-up report and submitted to UBC Pharmacovigilance according to the same timelines described above. The follow-up SAE report form must include the minimum information required for form completion and only changed/new information needs to be specified. Information provided in the follow-up SAE report form supersedes any information that was initially reported.

The SAE report form to be used in this study is provided as a separate document. All SAEs will also be recorded on the relevant CRF page, in addition to the SAE report form.

The Investigator or designee is responsible for submitting the relevant reports of SAEs that occur during the study to the local IEC, according to local regulations and in accordance with the respective safety management plan (SMP).

Confidentiality Statement

Data and information contained in this document are considered to constitute trade secrets and confidential commercial information, and the legal protections provided to such trade secrets and confidential information are hereby claimed under the provisions of applicable law. No part of this document may be publicly disclosed without the written consent of Philip Morris Products S.A.

8.4 Reporting of Other Events Critical to Safety Evaluations

8.4.1 Abnormal Results of Laboratory Tests

Any clinical safety laboratory test result that is outside of the normal reference range will be reviewed by the Investigator and assessed for clinical significance according to its severity. The severity of abnormal laboratory test result must be assessed using CTCAE version 4.03 grading scales (Appendix C). Any clinical safety laboratory test result that is outside of the normal reference range will be reviewed by the Investigator and assessed for clinical significance according to its severity. Whenever that grading scheme is not available for the laboratory result of concern, the Investigator should assess the severity and the clinical significance of that result using his/her medical judgment.

Subjects with clinically significant abnormal laboratory values at Screening will not be enrolled. Abnormal laboratory test results detected at the Screening Visit whose CTCAE grades are 2 or higher or still are CTCAE grade 1 and deemed clinically significant are usually concomitant disease or a manifestation of one and must be recorded accordingly. However, in some instances, they may be assessed as AEs (and therefore must be handled according to the directions in section 8.2) or as manifestations of already reported AEs. This decision will require a careful assessment of the abnormal result within the clinical context on a case-by-case basis and will depend on the Investigator's medical judgment.

Abnormal laboratory test results detected after the Screening Visit whose CTCAE grades are 2 or higher or still are CTCAE grade 1 and deemed clinically significant must be either recorded as AEs (and handled according to the directions in section 8.2) or linked to a concomitant disease or still to an already reported AE.

The principles for assessing and reporting abnormal laboratory test results, emerging after the Screening Visit, using CTCAE 4.03 grading scales are set up in Table 6:

Table 6 Principles for assessing and reporting abnormal laboratory test results

Grading	Clinically significant?	Is it a grade increase from previous results in study?§	Report?
Grade 1	No	Not applicable	No
Grade 1	Yes	No	No*
Grade 1	Yes	Yes	Yes, as AE or linked to an already reported AE
Grade 2 or higher	No/Yes	No	No*
Grade 2 or higher	No/Yes	Yes	Yes, as AE or linked to an already reported AE

Confidentiality Statement

Data and information contained in this document are considered to constitute trade secrets and confidential commercial information, and the legal protections provided to such trade secrets and confidential information are hereby claimed under the provisions of applicable law. No part of this document may be publicly disclosed without the written consent of Philip Morris Products S.A.

* in this situation, this abnormal lab test result is either a manifestation of a concomitant disease or of an already reported AE.

§ grade increase in this context means the value is higher than the one from the Screening Visit.

In general, laboratory values will be recorded as “increased <lab parameter>” or “decreased <lab parameter>” to ensure consistency of recording/coding.

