2.3.2 Anticipated Foreseeable Risks due to Study Procedures

The risk of scheduled procedures in the present study (e.g., blood samples) are deemed to be on par with procedures routinely performed during normal or extended health examinations by

Confidentiality Statement

Data and information contained in this document are considered to constitute trade secrets and confidential commercial information, and the legal protections provided to such trade secrets and confidential information are hereby claimed under the provisions of applicable law. No part of this document may be publicly disclosed without the written consent of Philip Morris Products S.A.

the subject's healthcare professional. The total volume of blood to be drawn is approximately 464 mL and does not exceed the levels for a standard blood donation. The risks related to blood sampling include for example: excessive bleeding, fainting, haematoma, paresthesia or infection, and those related to the total amount of blood taken over a period of time such as weakness, dizziness or anemia.

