7.6 Laboratory Assessments

7.6.1 Clinical Chemistry, Hematology, and Urine Analysis Safety Panel

A blood sample for hematology and clinical chemistry analysis will be taken from each subject at Screening, Admission and Day 2 to Day 5. Subjects should be fasting for at least 6 hours prior to sampling, except at Screening where non-fasting samples can be used. Tests will be conducted at a local laboratory (Appendix B). A urine sample will also be collected from each subject for urine analysis. Parameters to be tested are listed in Table 4.

Confidentiality Statement

Data and information contained in this document are considered to constitute trade secrets and confidential commercial information, and the legal protections provided to such trade secrets and confidential information are hereby claimed under the provisions of applicable law. No part of this document may be publicly disclosed without the written consent of Philip Morris Products S.A.

Table 4 Clinical Laboratory Parameters for Safety Panel

Hematology	Clinical Chemistry	Urine Analysis

 • Hematocrit • Hemoglobin • Mean corpuscular hemoglobin • Mean corpuscular hemoglobin concentration • Mean corpuscular volume • Platelet count • Red blood cell count • White blood cell (WBC) count • Differential WBC count: 
 • Neutrophils • Basophils • Eosinophils • Lymphocytes • Monocytes 	
 • Albumin • Total protein • Alkaline phosphatase • Alanine aminotransferase • Aspartate aminotransferase • Blood urea nitrogen • Creatinine • Gamma-glutamyl transferase • Fasting glucose* • Lactate dehydrogenase • Potassium • Sodium • Total bilirubin • Direct bilirubin • Total cholesterol • Triglycerides 	
 • pH • Bilirubin • Glucose • Nitrite • Red blood cell traces • Protein • Specific gravity

* Except at Screening where non-fasting glucose will be assessed

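### The Table 6 footnote defines a laboratory grade increase as a higher value than at Screening, which is wrong for low-direction parameters and contradicts the recording rule above the table

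*Protocol*

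**What the plan says.** Protocol section 8.4.1 gives the post-Screening rule twice.

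**The paragraph before Table 6.** It covers "Abnormal laboratory test results detected after the Screening Visit whose CTCAE grades are 2 or higher or still are CTCAE grade 1" and judged clinically significant. Such results "must be either recorded as AEs (and handled according to the directions in section 8.2) or linked to a concomitant disease" or to an AE already on record. It makes no distinction between high and low values. SAP section 12.6.5.4 repeats this rule and does not reproduce Table 6 or its footnote.

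**Table 6.** It asks three things: the CTCAE grade, whether the result is clinically significant, and "Is it a grade increase from previous results in study". A clinically significant grade 1 result, or any result of grade 2 or higher, is reported only if the third answer is yes. Otherwise the entry is `No*`, and the asterisk note says that "this abnormal lab test result is either a manifestation of a concomitant disease or of an already reported AE". The § note on the third column heading reads: "grade increase in this context means the value is higher than the one from the Screening Visit".

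The line after that note provides for AE terms in both an increased and a decreased form. Section 2.3.2 lists among the risks of blood sampling "those related to the total amount of blood taken over a period of time such as weakness, dizziness or anemia".

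**The concern.** A CTCAE grade measures severity, not the direction of the number. For a parameter graded on its fall, worsening means a lower value and a higher grade. A test that asks whether the value is higher than at Screening answers no to exactly the results that have become worse.

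AE data are the primary assessment of safety (protocol section 12.6.3). Laboratory AEs have their own planned summary, and each is assigned to the product used on the previous day. A laboratory AE that is wrongly omitted, or created by a trivial rise, therefore goes straight into the by-variant AE tables.

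**Working it through.** **1. How many graded parameters are affected.** Counting the rows of Appendix C by the direction in which the grade rises:

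| Table | Rows | Graded on a fall | Graded on a rise |
|---|---|---|---|
| C1 chemistry | 14 | 4 (sodium, potassium, glucose, albumin) | 10 |
| C2 haematology | 7 | 5 (haemoglobin, WBC, lymphocytes, neutrophils, platelets) | 2 |
| C3 urine | 1 | 0 | 1 |
| Total | 22 | 9 | 13 |

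9/22 = 41%.

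**2. What the footnote does to a falling value.** Table C2 grades low haemoglobin as Grade 1 from below the lower limit of normal (LLN) to 10.0 g/dL, Grade 2 below 10 to 8.0, and Grade 3 below 8.0. The documents give no LLN, so I assume 11.5 to 13.5 g/dL. I also assume 14 g/dL at Screening (Grade 0). The grades below hold across that whole LLN range.

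| Later value (g/dL) | Grade | Value higher than Screening? | Grade higher than Screening? | Table 6, literal footnote | Paragraph above Table 6 |
|---|---|---|---|---|---|
| 11 | 1 | No | Yes | `No*` if clinically significant | Record or link if clinically significant |
| 9.5 | 2 | No | Yes | `No*` | Record or link |
| 7.9 | 3 | No | Yes | `No*` | Record or link |

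The `No*` note presumes a concomitant disease or an AE already reported. For a new low value neither need exist.

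**3. What it does to a rising value.** Potassium that moves upward within its Grade 2 band (above 5.5 to 6.0 mmol/L) has a higher value but the same grade. Read literally, the footnote calls this a grade increase and Table 6 says to report it.

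**4. Footnote against its own column heading.** The heading asks about grade; the footnote asks about value. The heading compares with previous results in the study; the footnote compares with Screening. The two references can give different answers. A result that is Grade 2 at Screening, Grade 1 at Admission and Grade 2 again on Day 3 is an increase from the previous result but not from Screening.

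**5. The anaemia example and how far it goes.** Volumes per sample are in protocol section 7.7.1.

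- The plan's total: nicotine samples 4 × (10 + 8) + 5 = 77, and 77 × 5 mL = 385 mL. Adding 4 mL for CYP2A6 and 6 × 12.5 = 75 mL for safety panels gives 464 mL, as stated.
- Drawn before the Day 5 panel: Screening 12.5 + Admission 12.5 + Day 1 (18 × 5 + 4 = 94) + Days 2 to 4 (3 × (18 × 5 + 12.5) = 307.5) = 426.5 mL.
- Simple dilution, with an assumed blood volume BV: Hb after = Hb before × exp(−426.5/BV). For BV from 3.5 to 5.5 L the fall is about 11.5% down to 7.5%.
- From an assumed 11.0 g/dL: 9.74 at 3.5 L, 9.89 at 4.0 L, 10.10 at 5.0 L. Crossing below 10.0 needs BV under 426.5/ln(1.1), about 4.5 L.

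So blood sampling alone can move a subject from Grade 1 to Grade 2 only in part of the assumed range, and only from a low starting value.

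**The case against.** A reader might infer that worsening low values will simply not be reported as AEs. The documents do not support that.

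- The paragraph directly above Table 6, and SAP section 12.6.5.4, require such results to be recorded or linked.
- The asterisk note does not fit a new low value with no concomitant disease or prior AE.
- The recording convention provides for decreased parameters.
- Section 8.1.1 includes an abnormal laboratory finding in the definition of an AE, and section 8.4.1 has the Investigator review every out-of-range result.
- SAP section 12.6.5.4 lists CTCAE grades and provides shift tables, so the values stay visible as laboratory data.

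All of this stands.

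It can also be argued that the footnote means the grade when it says value, since it explains a grade increase in a table whose first column is the grading. On that reading the direction problem and the within-grade problem both disappear. The reading is plausible, but the sentence does not say it, and the table is introduced as setting the principles for assessing and reporting.

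The footnote may also be read as narrowing the heading to Screening, which is itself a previous result. That softens the conflict over the comparator but leaves the heading and the footnote worded differently.

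Finally, a reader might infer that Screening is the wrong comparator, because its panel may be non-fasting (Table 4 notes: "Except at Screening where non-fasting glucose will be assessed") and the SAP baseline for laboratory values is normally Admission (SAP section 4.1). That is a matter of choice. AE collection starts at consent (section 8.2.2), so Screening is a coherent reference for AE reporting, and the SAP baseline serves change-from-baseline summaries. The documents give no figure for how often a non-fasting Screening value would mask a later rise.

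**Conclusion.** The point holds as an internal contradiction with a wrongly worded footnote. Taken literally, the footnote gives the wrong answer for a worsening in any of 9 of the 22 graded Appendix C rows, and it counts within-grade rises as increases in high-direction rows. It conflicts with the mandatory paragraph in the same section and with SAP section 12.6.5.4, and it differs from its own column heading.

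The consequence is a risk of under-reporting low-direction laboratory AEs if a site works from Table 6 as written. It is not a demonstrated exclusion of such events. The count of 9 in 22 rests on Appendix C alone. The haemoglobin figures rest on assumed starting values, LLN and blood volume. They illustrate the rule and do not forecast what subjects will experience; Screening results judged clinically significant already bar enrolment.

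**What to change.** Reword the § note along these lines: *grade increase means that the CTCAE grade of the abnormality, in its own direction (high or low), is higher than the grade at the Screening Visit.* Change the third column heading of Table 6 to name the same comparator, and adjust the preceding paragraph so that the table and the text state one rule.

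Using the fasting Admission panel as comparator, to match the SAP baseline, is an optional further change and is not needed for this correction.

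The cost is one footnote, one column heading and a light edit to one paragraph. No samples are added, and SAP section 12.6.5.4 already has CTCAE grades derived by program. The downside is that a few more laboratory AEs may be recorded.
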